8.3.4. Concentration-QTc Analysis (Primary Analysis)

The relationship between LOXO-305 plasma concentrations and change from baseline QTc ($\Delta QTcF$ or ΔQTc corrected with the HR correction method chosen as primary if a substantial HR effect is observed) will be quantified using a linear mixed-effects modeling approach. The model will include ΔQTc as the dependent variable, LOXO-305 plasma concentrations as the explanatory variate (0 for placebo), centered baseline QTc (ie, baseline QTcF for individual subject minus the population mean baseline QTc for all subjects in the same treatment period) as an additional covariate, treatment (active = 1 or placebo = 0) and time (ie, nominal postdose timepoint) as fixed effects, and random effects on the intercept and slope per subject.¹⁸ In addition, if there are significant concentrations of LOXO-305 metabolites, their concentrations/QTc relationship may be explored (exploratory metabolite profiling has shown that unchanged LOXO-305 is the major drug-related component in human plasma).

The degrees of freedom of estimates will be determined by the Kenward-Roger method. From the model, the slope (ie, the regression parameter for LOXO-305 concentrations) and the treatment effect-specific intercept (defined as the difference between active and placebo)

will be estimated together with the 2-sided 90% CI. The estimates for the time effect will be reported with degrees of freedom and SE.

The geometric mean of the individual C_{max} values for subjects in the active dose group will be determined. The predicted effect and its 2-sided 90% CI for $\Delta\Delta QTc$ (ie, slope estimate \times concentration + treatment effect-specific intercept) at this geometric mean C_{max} of LOXO-305 will be obtained. If the upper bound of the 2-sided 90% CI of the predicted effect of $\Delta\Delta QTc$ at clinically relevant plasma levels of LOXO-305 is below 10 msec, it will be concluded that LOXO-305 does not cause clinically relevant QTc prolongation within the observed plasma concentration ranges.

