5.3 Baseline

For all continuous ECG parameters, baseline will be the average of the derived ECG intervals from the 3 time points (0.75, 0.5, and 0.25 hours) prior to treatment administration for each period on Day 1, Day 12, and Day 23, respectively. For T-wave morphology and U-wave presence, baseline includes findings observed in any of the replicates from the 3 time points prior to dosing for each period on Day 1, Day 12, and Day 23, respectively.

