6.2 Concentration-QTc Analysis (Primary Analysis)

The relationship between LOXO-305 plasma concentrations and change-from-baseline QTc ($\Delta QTcF$, or ΔQTc corrected with the HR correction method chosen as primary if a substantial HR effect is observed) be quantified using a linear mixed-effects modeling approach. The model will include ΔQTc as the dependent variable, LOXO-305 plasma concentrations as the explanatory variate (0 for placebo), centered baseline QTc (i.e., baseline QTc for individual subject minus the population mean baseline QTc for all subjects in the same treatment period) as an additional covariate, treatment (active = 1 or placebo = 0), time (i.e., nominal post-dose time point) as fixed effects, and random effects on the intercept and slope per subject¹. In addition, if there are significant concentrations of LOXO-305 metabolites, their concentrations/QTc relationship may be explored (exploratory metabolite profiling has shown that unchanged LOXO-305 is the major drug-related component in human plasma). In all calculations, zero will be substituted for concentrations below the quantification limit of the assay and for concentrations from subjects who received placebo.

An unstructured covariance matrix will be specified for the random effects. If convergence cannot be achieved even after appropriate rescaling of the concentrations, the random effect on the slope and intercept will be dropped, in this order, until convergence is achieved. The degrees of freedom of estimates will be determined by the Kenward-Roger method. From the model, the slope (i.e., the regression parameter for LOXO-305 concentrations) and the treatment effect-specific intercept (defined as the difference between active and placebo) will be estimated together with the 2-sided 90% CI. The estimates for the time effect will be reported with degrees of freedom and SE.

The geometric mean of the individual C_{max} values for subjects in the active dose group will be determined. The predicted effect and its 2-sided 90% CI for $\Delta\Delta QTc$ (i.e., slope estimate \times concentration + treatment effect-specific intercept) at this geometric mean C_{max} of LOXO-305 will be obtained. If the upper bound of the 2-sided 90% CI of the predicted effect of $\Delta\Delta QTc$ at clinically relevant plasma levels of LOXO-305 is below 10 ms, it will be concluded that LOXO-305 does not cause clinically relevant QTc prolongation within the observed plasma concentration ranges.

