To evaluate the adequacy of model fit with respect to the assumption of linearity, the observed ΔQTc values adjusted by population time effect estimated from the model will be used. These individual placebo-adjusted $\Delta QTc_{i,k}$ ($\Delta\Delta QTc_{i,k}$) values equal the observed individual $\Delta QTc_{i,k}$ for subject i administered with active drug or placebo at time point k minus the estimated population mean placebo effect at time point k (i.e., time effect). A quantile plot, i.e. plot of the quantiles (deciles) of observed drug concentrations and the mean placebo-adjusted ΔQTc ($\Delta\Delta QTc$) and 90% CI at the median concentration within each decile will be given. The regression line presenting the model-predicted $\Delta\Delta QTc$ (as described by Tornøe et al²) will be added to evaluate the fit of a linear model and visualize the concentration-response relationship. Additional exploratory analyses (via graphical displays and/or model fitting) will include assessing for a delayed effect (hysteresis, [Section 6.2.1](#)) and the justification for the choice of the pharmacodynamic model (linear versus nonlinear, [Section 6.2.2](#)) as follows.

The SAS code for the concentration-QTc analysis using the full model is as follows.

```
PROC MIXED DATA=PKPD method=reml;
CLASS SUBJID TIME;
MODEL DQTc=TRT CONC TIME CBASE/ solution cl noint alpha=0.1 alphap=0.1 COVB DDFM=KR;
RANDOM INT CONC /type=UN SUBJECT=SUBJID s;
RUN;
```

Where PKPD = PK/QTc population, SUBJID = subject number, TRT = treatment (active = 1 or placebo = 0), TIME = nominal post-dose time point, CONC = time-matched plasma concentration of LOXO-305 (0 for placebo), CBASE = centered baseline QTcF, and DQTc = Δ QTcF.

Note: ESTIMATE statements will be included for the prediction of the effect in the active dose group.

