6.3 Assay Sensitivity

The analysis to show assay sensitivity will be based on the concentration-QTc analysis of the effect on ΔQTc of 400 mg oral moxifloxacin using a similar model as for the primary analysis. That is, the relationship between moxifloxacin plasma concentration and ΔQTc will be investigated by linear mixed-effects modeling. The model will include ΔQTc as the dependent variable, moxifloxacin plasma concentration as the explanatory variable (0 for placebo), centered baseline QTc (i.e., baseline QTc for individual subject minus the population mean baseline QTc for all subjects in the same treatment period) as an additional covariate, study treatment (moxifloxacin = 1 or placebo = 0) and time (i.e., post-dose time point) as fixed effects, and a random intercept and slope per subject (Garnett et al¹). The geometric mean of the individual C_{max} values for subjects receiving the single dose of 400 mg moxifloxacin will be determined. The predicted effect and its 2-sided 90% CI for $\Delta\Delta QTc$ (i.e., slope estimate \times concentration + treatment effect-specific intercept) at this geometric mean C_{max} will be obtained.

If the slope of the moxifloxacin plasma concentration/ ΔQTc relationship is statistically significant at the 10% level in a 2-sided test and the lower bound of the 2-sided 90% CI of the predicted QT effect at the observed geometric C_{max} of the 400 mg dose is above 5 ms, assay sensitivity will be deemed to have been demonstrated.

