6.4 By-Time Point Analysis

The analysis for QTc will be based on a linear mixed-effects model with ΔQTc (ΔQTc_F , or ΔQTc corrected per the HR correction method chosen as primary if a substantial HR effect is observed) as the dependent variable, period, sequence, time (i.e., nominal post-dose time point), treatment (LOXO-305, moxifloxacin and placebo), and time-by-treatment interaction as fixed effects, and baseline QTc as a covariate. An unstructured covariance matrix will be specified for the repeated measures at post-dose time points for subject within treatment period. If the model with unstructured covariance matrix fails to converge, other covariance matrix such as compound symmetry and autoregressive will be considered. The model will also include a subject-specific random effect. If the fixed effects for period and/or sequence should prove to be nonsignificant (that is, if the P value > 0.1), these effects may be removed from the model and the analysis will be repeated without those covariates. From this analysis, the LS mean, SE, and 2-sided 90 % CI will be calculated for the contrast “LOXO-305 versus placebo” at each post-dose time point, separately.

For HR, PR, QRS intervals, and QTc with the methods not selected as primary, the analysis will be based on the change-from-baseline post-dosing values (ΔHR , ΔPR , ΔQRS , and ΔQTc). The same (by-time point analysis) model will be used as described above for QTc. The LS mean, SE, and 2-sided 90% CI from the statistical modeling for both change-from-baseline and placebo-corrected change-from-baseline values will be listed in the tables and graphically displayed.

The SAS code for the by-time point analysis for QTc is as follows.

```
PROC MIXED DATA=ECG;  
CLASS SUBJID TREAT TIME PERIOD SEQUENCE;
```

```
MODEL DQTc=BASE TREAT TIME TREAT*TIME PERIOD SEQUENCE/DDFM=KR;  
RANDOM INTERCEPT / SUBJECT =SUBJID TYPE=UN;  
REPEATED TIME / SUBJECT = PERIOD*SUBJID TYPE = UN;  
LSMEANS TREAT*TIME/CL DIFF ALPHA=0.1;  
RUN;
```

Where ECG = QT/QTc population, SUBJID = subject number, TREAT = treatment (LOXO-305, moxifloxacin and placebo), TIME = nominal post-dose time point, BASE = baseline QTc, PERIOD = period, SEQUENCE = sequence, and DQTc = Δ QTc.

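### The LOXO-305 and moxifloxacin concentration-QTc models have no PERIOD term, although the trial is a three-period crossover and the by-time point model has one; adding it is nearly free.

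*SAP*

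**What the plan says.** The trial randomises subjects to six sequences over three periods, dosed on Days 1, 12 and 23.

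- **Primary model, SAP 6.2.** The fixed part is "MODEL DQTc=TRT CONC TIME CBASE/ solution cl noint alpha=0.1 alphap=0.1 COVB DDFM=KR" and the random part is "RANDOM INT CONC /type=UN SUBJECT=SUBJID s". Neither contains period.
- **Protocol 8.3.4.** Besides concentration and centred baseline it lists "treatment (active = 1 or placebo = 0) and time (ie, nominal postdose timepoint) as fixed effects". Period is absent here too, so the two documents agree.
- **Moxifloxacin model, SAP 6.3.** It has the same structure, with "a random intercept and slope per subject" and no period term.
- **By-time point model, SAP 6.4.** The code is "MODEL DQTc=BASE TREAT TIME TREAT*TIME PERIOD SEQUENCE/DDFM=KR". If period or sequence has a P value above 0.1, "these effects may be removed from the model and the analysis will be" repeated without them.
- **Baseline, SAP 5.3.** It is the mean of three time points "prior to treatment administration for each period on Day 1, Day 12, and Day 23, respectively". The covariate in SAP 6.2 is "baseline QTc for individual subject minus the population mean baseline QTc for all subjects in the same treatment period".

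Neither document explains why period is in one model and not in the other. No sensitivity analysis of the primary model with period is planned, and the residual plots in SAP 6.2.2 do not include one by period.

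**The concern.** Within each subject, LOXO-305 and placebo are given in different periods. If the post-dose change from baseline shifts from period to period for reasons unrelated to drug, that shift enters each subject's LOXO-305 minus placebo difference. The random effects are a subject intercept and a concentration slope, so the shift has nowhere to go except the slope variance and the residual. With equal numbers per sequence it averages out of the estimate but still widens the interval. With unequal numbers part of it stays in the estimate. The same holds for moxifloxacin minus placebo, on which the assay-sensitivity claim rests.

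**Working it through.** **Inputs.** From SAP 6.8: 24 evaluable subjects, true effect 3 ms, margin 10 ms, SD of ΔQTc 8 ms on each treatment, one-sided 5%, paired t-test, 30 enrolled at 5 per sequence. From SAP 6.8.1: moxifloxacin SE 1.24 ms with 24 subjects, assumed effect 10 ms, threshold 5 ms. Assumed, because the documents give no value: a linear drift of d ms per period in ΔQTc, common to all subjects and time points, with d from 1 to 4.

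**1. The plan's power.** With uncorrelated treatments the SD of the difference is 8 × √2 = 11.31 ms, so SE = 11.31/√24 = 2.31 ms. The noncentral t with 23 df and noncentrality 7/2.31 gives 90.2%. The stated figure of at least 90% is reproduced.

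**2. Drift in QTc level.** ΔQTc is taken from the same period's baseline and the covariate is centred within period, so a level shift cancels. In simulated trials under the SAP model, a 3 ms per period level drift left the estimate and SE unchanged.

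**3. Drift in ΔQTc, balanced sequences.** The LOXO-305 minus placebo period offsets for ABC, BCA, CAB, ACB, CBA and BAC are −d, +2d, −d, −2d, +d, +d. They sum to 0 and their mean square is 12d²/6 = 2d². Without PERIOD the reported SE is about √(128/24 + 2d²/23):

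| d (ms per period) | SE (ms) | Power | Rise in upper bound (ms) |
|---|---|---|---|
| 0 | 2.31 | 90.2% | 0 |
| 1 | 2.33 | 89.8% | 0.03 |
| 2 | 2.38 | 88.6% | 0.13 |
| 3 | 2.47 | 86.5% | 0.28 |
| 4 | 2.59 | 83.5% | 0.49 |

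With PERIOD, SE stays at 2.31 with 21 df, and power is 90.1% whatever the drift.

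The power column treats the offsets as extra random noise. Under exact balance they do not change the true spread of the estimate, so it somewhat overstates the loss. Simulating the paired t-test directly with fixed, balanced offsets (400,000 trials) gave about 90.1%, 89.2%, 87.9% and 86.2% for d = 1 to 4.

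**4. The mixed model itself.** This used 60 simulated trials per setting, model-based SE without Kenward-Roger, and assumed PK and variance components. At d = 2 the mean SE without PERIOD rose from 1.44 to 1.59 ms with a between-period SD of 4 ms, and from 0.57 to 0.86 ms with a between-period SD of 0. With PERIOD it was 1.41 and 0.55 ms. The actual spread of the estimate hardly moved (1.24 to 1.26, and 0.59 to 0.62). The inflation is therefore in the reported SE, and it is proportionally larger when the true variability is small.

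**5. Moxifloxacin.** The moxifloxacin minus placebo offsets are +d, +d, −2d, −d, −d, +2d, again with mean square 2d². At d = 2, SE = √(1.24² + 8/23) = 1.37 ms. Power to clear 5 ms goes from 98.8% (noncentrality 5/1.24) to about 97% (5/1.37).

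**6. Uneven drop-out.** Bias equals the mean offset among those retained. For 6 random losses from 30, its SD is √[(2d² × 30/29) × (1 − 24/30)/24] = 0.13d, and at least 95% of draws lie within ±0.25d. At d = 2 that is 0.26 ms and 0.5 ms. The worst possible 24 of 30 gives 0.46d, or 0.92 ms. In that case the simulated estimate was 4.29 ms without PERIOD and 3.42 ms with it.

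**The case against.** Much of the case for leaving the model alone stands. The protocol and SAP specify the same model, so there is no contradiction to repair. The by-time point model keeps period only conditionally. No drift is documented, and on the planning SD a 2 ms per period drift costs under 2 points of power and 0.13 ms on the upper bound. In the balanced case the wider interval is conservative for the primary claim.

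Three stronger readings are tempting, and the documents do not support them.

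- **That any drift between periods harms the analysis.** It does not. The period-specific baseline and the within-period centring deal with drift in QTc level.
- **That the upper bound will miss the truth more than 5% of the time.** This needs both drift and a rare split. With 5/3/5/5/3/3 completers in the sequence order above, the bias is −8d/24, or −0.67 ms at d = 2. In one set of 400 simulated trials the miss rate was then 9.5%, against 5.0% with PERIOD. An imbalance that large arises in about 1.4% of random losses of 6 from 30, and in the harmful direction in about 0.7%. When sequences are balanced, drift pushes the miss rate below 5%.
- **That balance is lost by design.** The sponsor may replace withdrawn subjects, and subjects with one usable period stay in the PK/QTc population. Removing whole subjects, as in step 6, is a simplification.

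The objection does not give a reason for the omission. Balance protects the estimate but not the SE. Replacement is discretionary, and nothing planned would show the drift if it occurred.

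**Conclusion.** The omission is real and unexplained, and its likely effect is small. With balanced sequences, a drift in change-from-baseline QTc inflates the reported SE. Planning power moves from 90.2% to between 89.8% and 83.5% for 1 to 4 ms per period, and somewhat less on the direct simulation. For moxifloxacin at 2 ms per period the SE moves from 1.24 to about 1.37 ms. With uneven drop-out the estimate can be biased either way, typically by under 0.5 ms at 2 ms per period. All of this rests on assumed drift sizes, a linear drift common to all subjects, and random loss of whole subjects. It is a low-severity improvement, worth making because it costs almost nothing. It is not evidence that the primary conclusion would be wrong.

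**What to change.** Add PERIOD to the CLASS and MODEL statements of both concentration-QTc models, for example `MODEL DQTc=TRT CONC TIME PERIOD CBASE` with the existing options, and make the matching change to the text of SAP 6.2 and 6.3. Pre-specify it and keep it whatever its P value.

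No special coding of PERIOD is needed for the primary result, because the treatment intercept plus slope × Cmax does not depend on how an additive period factor is coded. The TIME estimates do depend on it. The SAP should therefore say that they are reported averaged over periods, and that the placebo-adjusted values in SAP 6.2 and 6.7 also allow for period. A box plot of residuals by period would be a useful addition to SAP 6.2.2.

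The cost is one class term, 2 degrees of freedom and, with no drift, about 0.1 point of power (90.1% against 90.2%). If the sponsor prefers to keep the primary model as it is, the minimum is a pre-specified sensitivity analysis with PERIOD for both drugs.

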6.2.1 Investigation of Hysteresis

Hysteresis will be assessed based on joint graphical displays of the least squares (LS) mean $\Delta\Delta$ QTc at each post-dose time point from the by-time point analysis and the mean concentrations of LOXO-305 at the same time points. In addition, hysteresis plots will be given for LS mean $\Delta\Delta$ QTc from the by-time point analysis and the mean concentrations. Other concentration-QTc models may be explored if both of the following conditions are met.

- A QT effect > 10 ms (i.e., LS mean $\Delta\Delta$ QTc > 10 ms) cannot be excluded in the by-time point analysis
- The difference (delay) between the time to reach the peak QTc effect ($\Delta\Delta$ QTc) and t_{max} is larger than 1 hour.

With the provision stated above, hysteresis will be assumed if the curve of the hysteresis plot shows a counterclockwise loop. A significant treatment effect-specific intercept may also be indicative of hysteresis or model misspecification, if it cannot be explained by a nonlinear relationship.

6.2.2 Appropriateness of a Linear Model

To assess the appropriateness of a linear model, normal quantile-quantile (Q-Q) plots for the standardized residuals and the random effects; scatter plots of standardized residuals versus concentration, fitted values, and centered baseline QTc; and box plots of standardized residuals versus nominal time, and active treatment will be produced, in addition to the quantile plot described above. Among these plots, the scatter plots of standardized residuals versus concentration and versus centered baseline QTc will also include the locally weighted scatter plot smoothing (LOESS) lines with optimal smoothing parameters selected by the Akaike information criterion with a correction (AICC)^{3,4}. A scatter plot of observed concentration and Δ QTcF with a LOESS smooth line with 90% CI and a linear regression line will also be provided to check the assumption of a linear concentration-QTc relationship. If there is an indication that a linear model is inappropriate, additional models may be fitted, specifically an E_{max} model. The concentration-QTc analysis will then be repeated for the model found to best accommodate the nonlinearity detected.

6.3 Assay Sensitivity

The analysis to show assay sensitivity will be based on the concentration-QTc analysis of the effect on ΔQTc of 400 mg oral moxifloxacin using a similar model as for the primary analysis. That is, the relationship between moxifloxacin plasma concentration and ΔQTc will be investigated by linear mixed-effects modeling. The model will include ΔQTc as the dependent variable, moxifloxacin plasma concentration as the explanatory variable (0 for placebo), centered baseline QTc (i.e., baseline QTc for individual subject minus the population mean baseline QTc for all subjects in the same treatment period) as an additional covariate, study treatment (moxifloxacin = 1 or placebo = 0) and time (i.e., post-dose time point) as fixed effects, and a random intercept and slope per subject (Garnett et al¹). The geometric mean of the individual C_{max} values for subjects receiving the single dose of 400 mg moxifloxacin will be determined. The predicted effect and its 2-sided 90% CI for $\Delta\Delta QTc$ (i.e., slope estimate \times concentration + treatment effect-specific intercept) at this geometric mean C_{max} will be obtained.

If the slope of the moxifloxacin plasma concentration/ ΔQTc relationship is statistically significant at the 10% level in a 2-sided test and the lower bound of the 2-sided 90% CI of the predicted QT effect at the observed geometric C_{max} of the 400 mg dose is above 5 ms, assay sensitivity will be deemed to have been demonstrated.

6.4 By-Time Point Analysis

The analysis for QTc will be based on a linear mixed-effects model with ΔQTc (ΔQTc_F , or ΔQTc corrected per the HR correction method chosen as primary if a substantial HR effect is observed) as the dependent variable, period, sequence, time (i.e., nominal post-dose time point), treatment (LOXO-305, moxifloxacin and placebo), and time-by-treatment interaction as fixed effects, and baseline QTc as a covariate. An unstructured covariance matrix will be specified for the repeated measures at post-dose time points for subject within treatment period. If the model with unstructured covariance matrix fails to converge, other covariance matrix such as compound symmetry and autoregressive will be considered. The model will also include a subject-specific random effect. If the fixed effects for period and/or sequence should prove to be nonsignificant (that is, if the P value > 0.1), these effects may be removed from the model and the analysis will be repeated without those covariates. From this analysis, the LS mean, SE, and 2-sided 90 % CI will be calculated for the contrast “LOXO-305 versus placebo” at each post-dose time point, separately.

For HR, PR, QRS intervals, and QTc with the methods not selected as primary, the analysis will be based on the change-from-baseline post-dosing values (ΔHR , ΔPR , ΔQRS , and ΔQTc). The same (by-time point analysis) model will be used as described above for QTc. The LS mean, SE, and 2-sided 90% CI from the statistical modeling for both change-from-baseline and placebo-corrected change-from-baseline values will be listed in the tables and graphically displayed.

The SAS code for the by-time point analysis for QTc is as follows.

```
PROC MIXED DATA=ECG;  
CLASS SUBJID TREAT TIME PERIOD SEQUENCE;
```

```
MODEL DQTc=BASE TREAT TIME TREAT*TIME PERIOD SEQUENCE/DDFM=KR;  
RANDOM INTERCEPT / SUBJECT =SUBJID TYPE=UN;  
REPEATED TIME / SUBJECT = PERIOD*SUBJID TYPE = UN;  
LSMEANS TREAT*TIME/CL DIFF ALPHA=0.1;  
RUN;
```

Where ECG = QT/QTc population, SUBJID = subject number, TREAT = treatment (LOXO-305, moxifloxacin and placebo), TIME = nominal post-dose time point, BASE = baseline QTc, PERIOD = period, SEQUENCE = sequence, and DQTc = Δ QTc.

